7. EFFICACY ASSESSMENTS

7.1. Primary Efficacy Endpoint

The primary efficacy endpoint is ORR assessed by independent central imaging facility review based on RECIST version 1.1. Refer to Section [17.3](#) for details regarding RECIST for radiological tumor assessments.

7.2. Secondary Efficacy Endpoints

Secondary efficacy endpoints include duration of response, best percent change in the SLD of measurable tumors, DCR, clinical benefit ratio (CBR), PFS, OS, and ORR assessed by the investigator based on RECIST version 1.1.

7.3. Exploratory Efficacy Endpoints

Exploratory efficacy endpoints include duration of stable disease, time to response, evaluation of exposure-response relationships for efficacy and safety endpoints, and potential biomarkers of response, such as serum HER2ECD concentrations.

8. PHARMACOKINETIC/PHARMACODYNAMIC ASSESSMENTS

8.1. Pharmacokinetic (PK)

Blood samples for DS-8201a PK analyses will be obtained at the time points specified in the Schedule of Events (Table 6.1 and Table 6.2) and in Table 8.1 and Table 8.2 below.

Table 8.1: Blood Sampling for PK Analysis – Part 1 PK Stage

Cycle	Day	Sampling Time Point (Acceptable Ranges)
Cycle 1	Day 1	BI (– 8 hours) EOI: Within 15 minutes after EOI 2 hours after the start of drug administration (± 15 minutes) 4 hours after the start of drug administration (± 15 minutes) 7 hours after the start of drug administration (± 15 minutes)
	Day 2	24 hours after the start of drug administration (± 2 hours)
	Day 4	72 hours after the start of drug administration (± 2 hours)
	Day 8	7 days after the start of drug administration (± 1 day)
	Day 15	14 days after the start of drug administration (± 1 day)
	Day 22	If the schedule on Day 1 of the next cycle is delayed for 3 days or more, including if the subject cannot continue onto the next cycle, collect blood sample 21 days after the start of drug administration (± 2 days)
Cycle 2	Day 1	BI (– 8 hours) If blood sample is collected on Day 22 of Cycle 1, the blood sample will be collected at BI on Day 1 of Cycle 2. EOI: Within 15 minutes after EOI
	Day 22	If the schedule on Day 1 of the next cycle is delayed for 3 days or more, including if the subject cannot continue onto the next cycle, collect blood sample on 21 days after the start of drug administration (± 2 days)
Cycle 3	Day 1	BI (– 8 hours) If blood sample is collected on Day 22 of Cycle 2, the blood sample will be collected at BI on Day 1 of Cycle 3. EOI: Within 15 minutes after EOI 4 hours after the start of drug administration (± 15 minutes) 7 hours after the start of drug administration (± 15 minutes)
	Day 22	If the schedule on Day 1 of the next cycle is delayed for 3 days or more, including if the subject cannot continue onto the next cycle, collect blood sample on 21 days after the start of drug administration (± 2 days)

Cycle	Day	Sampling Time Point (Acceptable Ranges)
Cycle 4, 6, 8	Day 1	BI (– 8 hours) If blood sample is collected on Day 22 of Cycle 3, the blood sample will be collected at BI on Day 1 of Cycle 4. EOI: Within 15 minutes after EOI

BI = before infusion; EOI = end of infusion.

Table 8.2: Blood Sampling for PK Analysis – Part 1 Dose Finding and Part 2

Cycle	Day	Sampling Time Point (Acceptable Range)
Cycle 1	Day 1	BI (– 8 hours) EOI: Within 15 minutes after EOI 4 hours after the start of drug administration (\pm 15 minutes) 7 hours after the start of drug administration (\pm 15 minutes)
	Day 8	7 days after the start of drug administration (\pm 1 day)
	Day 15	14 days after the start of drug administration (\pm 1 day)
	Day 22	If the schedule on Day 1 of the next cycle is delayed for 3 days or more, including if the subject cannot continue onto the next cycle, collect blood sample 21 days after the start of drug administration (\pm 2 days)
Cycle 2	Day 1	BI (– 8 hours) If blood sample is collected on Day 22 of Cycle 1, the blood sample will be collected at BI on Day 1 of Cycle 2. EOI: Within 15 minutes after EOI
	Day 22	If the schedule on Day 1 of the next cycle is delayed for 3 days or more, including if the subject cannot continue onto the next cycle, collect blood sample on 21 days after the start of drug administration (\pm 2 days)
Cycle 3	Day 1	BI (– 8 hours) If blood sample is collected on Day 22 of Cycle 2, the blood sample will be collected at BI on Day 1 of Cycle 3. EOI: Within 15 minutes after EOI 4 hours after the start of drug administration (\pm 15 minutes) 7 hours after the start of drug administration (\pm 15 minutes)
	Day 22	If the schedule on Day 1 of the next cycle is delayed for 3 days or more, including if the subject cannot continue onto the next cycle, collect blood sample on 21 days after the start of drug administration (\pm 2 days)

Cycle	Day	Sampling Time Point (Acceptable Range)
Cycle 4, 6, 8	Day 1	BI (– 8 hours) If blood sample is collected on Day 22 of Cycle 3, the blood sample will be collected at BI on Day 1 of Cycle 4. EOI: Within 15 minutes after EOI

BI = before infusion; EOI = end of infusion.

At each time point, blood will be collected for DS-8201a analysis. The actual time of study drug administration and the exact time of blood sampling for DS-8201a PK analysis must be recorded on the electronic case report form (eCRF).

Instructions for the handling of blood samples and shipping of serum samples for DS-8201a PK analyses are included in a separate document (ie, Laboratory Manual). The DS-8201a PK samples will be shipped to a central laboratory for forwarding to a Sponsor designated bioanalytical laboratory.

Serum concentrations of DS-8201a, total anti-HER2 antibody and MAAA-1181a will be measured using validated assays at the bioanalytical laboratory.

The serum PK parameters (listed in Section 2.3.2) for DS-8201a, total anti-HER2 antibody and MAAA-1181a for each subject will be estimated using standard noncompartmental method.

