1.1.1.2. Description

DS-8201a consists of an antibody component, MAAL-9001, covalently conjugated via a maleimide tetrapeptide linker, to a drug component MAAA-1181a. MAAL-9001 is an in-house humanized immunoglobulin G1 (IgG1) monoclonal antibody having the same amino acid sequence as trastuzumab. MAAA-1181a, an exatecan derivative,^{4,5,6} is a topoisomerase I inhibitor, cell-membrane permeable, and more potent than SN-38 (active metabolite of irinotecan). This ADC achieves a high drug-to-antibody ratio (DAR) (7 to 8) with homogeneous conjugation with MAAA-1181a.⁷ DS-8201a is cleaved by lysosomal enzymes and releases MAAA-1181a in the cytoplasm after it binds to HER2 receptor and gets internalized in tumor cells.

The DS-8201a Phase 1 clinical study DS8201-A-J101 was initiated with the antibody component, MAAL-9001, [REDACTED] (drug substance 1 [DS 1]). To support new clinical studies, [REDACTED], transition is being made to MAAL-9001 [REDACTED] (DS 2). Analytic comparison of the two [REDACTED] products has shown comparability across a wide range of variables. [REDACTED]

[REDACTED] Following single IV administration of DS-8201a to cynomolgus monkeys, mean maximum plasma/serum concentration C_{max} of DS-8201a was similar, while area under the concentration-time curve (AUC) was approximately 15% lower, for DS 2 material as compared to DS 1 material. However, in a xenograft study, no difference was seen in cytotoxicity between the two products. Further analysis to assess the

comparability of FL-DP2 used in this study to FL-DP1 data reported from the DS8201-A-J101 study will be performed as detailed in Section 1.2.

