DS8201-A-U201 is designed in three stages to determine the efficacy of the recommended Phase 2 dose (RP2D) for FL-DP2 and Lyo-DP drug product in this population. In the first stage, three dose levels, 5.4, 6.4, and 7.4 mg/kg were selected for comparison with the FL-DP1 drug product doses (5.4 mg/kg and 6.4 mg/kg) used in the Phase 1 trial. As described in Section 1.1.1.2, non-clinical comparative evaluation suggested no apparent difference in antitumor activity between FL-DP1 material and FL-DP2 material was detected in a xenograft mouse model. The [REDACTED] L-DP1 doses (5.4 mg/kg and 6.4 mg/kg) investigated in the Phase 1 expansion will therefore be used at the start of DS8201-A-U201. Considering the lower AUC observed in monkeys for FL-DP2 material as compared to FL-DP1, a higher dose of 7.4 mg/kg will be added as a third dose for investigation. Therefore, in the PK Stage, DS-8201a with FL-DP2 material will be administered at 5.4, 6.4 or 7.4 mg/kg to approximately 20 subjects per dose. PK samples will be collected and two doses, with PK profiles matching those from the administration of 5.4 and 6.4 mg/kg with FL-DP1 material in study DS8201-A-J101, will be selected for further evaluation in the Dose Finding Stage.

In the second stage, a second dose selection analysis will be conducted. This population PK and exposure-response analysis will be conducted, utilizing all available PK, efficacy (tumor size and ORR) and safety (thrombocytopenia and neutropenia) data from both PK, Dose Finding Stages and study DS8201-A-J101 to select the final RP2D for evaluation.

█-DP2 █ will be supplied at the start of the trial with a planned transition to █-DP █ material once █ becomes available. This transition is expected to occur at approximately the start of Part 2 of this trial.

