11.4.2. Pharmacokinetic/Pharmacodynamic Analyses

11.4.2.1. Pharmacokinetic Analyses

Serum concentrations for DS-8201a, total anti-HER2 antibody and MAAA-1181a will be listed, plotted, and summarized using descriptive statistics by Part (and Stage)/dose level/study day at each time point. PK parameters will be listed and summarized using descriptive statistics by Part (and Stage)/dose level. A dose selection analysis will also be conducted based on the data from Part 1, and based on comparative PK results, 2 doses will be selected for dose-finding stage of Part 1.

The population pharmacokinetic and exposure-response analysis will be conducted for all evaluable subjects in the study. An interim population PK and exposure response analysis may also be conducted based on the data from Part 1. Modeling results will be presented in separate reports.

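### Dose Finding and Part 2 take no Cycle 1 PK sample between 7 hours and Day 8, so their noncompartmental AUC is biased upward and not comparable with the densely sampled PK Stage

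*Combined protocol and SAP*

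**What the plan says.** Cycle 1 sampling in the PK Stage (Table 8.1) is pre-dose, end of infusion, 2, 4 and 7 h, then "24 hours after the start of drug administration" and "72 hours after the start of drug administration", then Days 8 and 15 and the 21-day point. Table 8.2 covers the Dose Finding Stage and Part 2. Its last Day 1 sample is "7 hours after the start of drug administration" and the next is "7 days after the start of drug administration"; the 2, 24 and 72 h samples are absent. Section 6.4.1 and Table 6.2 agree.

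Section 8.1 then gives one rule for everyone: the Section 2.3.2 parameters "for each subject will be estimated using standard noncompartmental method". For Cycle 1 these include AUClast and AUC0-21d without qualification; AUCinf, T1/2, CL and Vss are to be given where appropriate. No trapezoidal rule is named.

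Section 11.4.2.1 provides that "PK parameters will be listed and summarized using descriptive statistics by Part (and Stage)/dose level", without a caveat on comparing stages. The same section plans a population PK analysis of all evaluable subjects, but does not say that it replaces the noncompartmental tables.

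**The concern.** Noncompartmental AUC is the area under straight or log-linear segments joining the observed points. It is accurate only where samples follow the shape of the curve. If concentration falls quickly and then slowly between two samples, a single segment across the interval lies above the curve and the area is too large. Here the unsampled interval runs from 7 h to about 168 h, which would contain most of an early distribution phase.

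Cycle 1 PK parameters are secondary endpoints and PK is a secondary objective. Printed by Part and Stage, the same quantity would carry a different systematic error in the PK Stage row than in the rows below it. A reader could take the step for a difference in exposure.

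**Working it through.** **Inputs.** Table 1.1 at 5.4 mg/kg: Cmax 127 µg/mL, AUC0-21d 542 and AUCinf 590 µg·day/mL, T1/2 6.03 days. First infusion 90 min (Section 5.2.4), so T = 0.0625 day. Assumed: biexponential decline, nominal sampling times, and a 21-day (Day 22 or Cycle 2 pre-dose) sample under both schedules. The documents give no figure for the sampling effect itself.

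**Is the decline single-phase?** If it were, AUCinf would be about Cmax × T1/2 / ln 2 = 127 × 6.03 / 0.693 = 1105. Table 1.1 reports 590, so a fast early phase is needed.

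**Reproducing the plan's figure.** A biexponential set from Cmax, AUCinf, T1/2 and Vss, with AUC0-21d left out, predicts AUC0-21d of 540 to 546 at 5.4 mg/kg against 542 in Table 1.1. The curve type is adequate for this purpose.

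**Fit to Cmax, AUC0-21d, AUCinf and T1/2.**
- β = ln 2 / 6.03 = 0.115 per day.
- C(21 d) = (590 − 542) × β = 5.5.
- B, carried back to end of infusion, = 5.5 × exp(β × 20.94) = 61.2.
- A = 127 − 61.2 = 65.8.
- α = 1.23 per day, chosen so that total area is 590.

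**The gap itself.** The curve gives 109.2 at 7 h, 75.7 at 24 h, 45.4 at 72 h and 27.6 at 168 h. The interval from 7 h to 168 h is 6.708 days.
- True area: (49.6 − 0.0)/1.234 + (59.6 − 27.6)/0.1149 ≈ 319.
- One linear segment: 6.708 × (109.2 + 27.6)/2 ≈ 459.
- One log segment: 6.708 × (109.2 − 27.6)/ln(109.2/27.6) ≈ 398.
- With the 24 h and 72 h points: about 333 (linear) or 326 (log).

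**Whole AUC0-21d (true value at 5.4 mg/kg 542, at 6.4 mg/kg 900).**

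| Dose | Rule | Table 8.1 times | Table 8.2 times | Ratio |
|---|---|---|---|---|
| 5.4 mg/kg | linear | 566 | 692 | 1.22 |
| 5.4 mg/kg | linear-up/log-down | 549 | 621 | 1.13 |
| 6.4 mg/kg | linear | 932 | 1103 | 1.18 |
| 6.4 mg/kg | linear-up/log-down | 911 | 1014 | 1.11 |

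At 5.4 mg/kg the dense schedule is within 1% to 4% of the true area (549/542, 566/542). The sparse schedule is 15% to 28% above it (621/542, 692/542).

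**CL, if reported.** Adding the same tail of 48 to each, AUCinf is 614 against 740 (linear) or 597 against 669 (log-down). CL is dose/AUCinf, so sparse CL is 614/740 = 0.83 or 597/669 = 0.89 of dense CL.

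**Sensitivity of the 5.4 mg/kg AUC ratio.**
- Calibrated to Vss instead of AUC0-21d: +9% to +20%.
- Total antibody (Table 1.2): +9% to +15%.
- MAAA-1181a (Table 1.3, rough fit): +12% to +26%.
- Parameters varied between subjects by the Table 1.1 standard deviations, the early half-life drawn between 0.3 and 1.5 days, and Days 8 and 15 moved within ±1 day: mean +10.1% (5th to 95th percentile 2.0 to 23.1) with log-down, and +22.3% (5.5 to 47.4) with linear.

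The sign was upward in every biexponential case tried.

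**The case against.** The strongest reply is that little rests on these tables. They are descriptive, the stages are shown separately, and no test or equivalence claim between them is planned. The first dose selection (Section 11.5) uses the serially sampled PK Stage. For the second, Section 1.2 calls for population PK and exposure-response modelling, which can handle sparse data. AUCinf, T1/2, CL and Vss may be withheld where the data do not support them. All of this stands, and it makes the point minor. It does not cover AUClast and AUC0-21d, which are unqualified secondary endpoints.

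Four stronger readings are tempting, and the documents do not support them.

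- **That the sampling change coincides with the product change, so a real fall in Part 2 exposure could be hidden.** Sampling thins between the PK Stage and Dose Finding. The product change comes later: "This transition is expected to occur at approximately the start of Part 2 of this trial". About 30 Dose Finding subjects and about 100 Part 2a subjects at 5.4 mg/kg therefore lie on either side of the expected transition under one schedule. On the fitted curve, a true 15% drop compared sparse with sparse reads as −15% if concentrations scale down, and about −11% to −14% if elimination is faster. Only a reader comparing Part 2 with the PK Stage would be misled.
- **That the artefact should be judged against a 15% product difference.** Section 1.1.1.2 reports that "area under the concentration-time curve (AUC) was approximately 15% lower, for DS 2 material as compared to DS 1 material", in monkeys. That question belongs to FL-DP2 versus FL-DP1 and is addressed in the PK Stage. Section 1.2 describes FL-DP2 and Lyo-DP as sharing a formulation and differing mainly in dosage form.
- **That the sparse schedule misses the MAAA-1181a peak.** The Tmax of 23.76 h in Table 1.3 is the upper end of a range in 6 subjects. The central value is 5.28 h, which the 4 h and 7 h samples bracket.
- **That a dose decision is compromised.** None is shown to use sparse noncompartmental AUC.

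**Conclusion.** The point holds in a limited form and is minor. Followed as written, the plan produces Dose Finding and Part 2 AUC values that are biased upward, and CL values, if given, that are biased downward. Neither is comparable with the PK Stage. At 5.4 mg/kg, the Part 2 dose, the AUC excess of sparse over dense is about 13% to 22%, or about 9% to 20% under the alternative calibration.

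The direction follows from Table 1.1 and the sampling tables. The size is a model estimate: it assumes biexponential decline, Phase 1 means from 6 subjects given FL-DP1 material (AUC0-21d standard deviation 163 on a mean of 542), and one of two usual trapezoidal rules, since none is named. I have not worked out a direction for Vss. Observed DS-8201a Cmax is little affected. Dose Finding versus Part 2 at the same dose is not confounded by the sampling change.

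**What to change.** In Sections 8.1 and 11.4.2.1, limit noncompartmental AUC, CL and Vss to the PK Stage. Report Cycle 1 exposure in Dose Finding and Part 2 as model-predicted values from the population PK analysis already planned.

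If noncompartmental AUC is still to be shown across stages:
- recompute the PK Stage values on the post-dose times common to both schedules (end of infusion, 4 h, 7 h, Days 8, 15 and 22), noting that this restores comparability but leaves both sets biased upward;
- name the trapezoidal rule;
- make any comparison across the product transition Dose Finding versus Part 2 at the same dose.

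The cost is analysis wording only: no added samples, visits or models. The downside is that the sparsely sampled stages lose a stand-alone noncompartmental AUC table. A footnote warning against comparing PK Stage and later AUC would be cheaper still and would prevent the misreading, but it would leave the biased values in the report.

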8.2. Pharmacodynamic

Not Applicable.

8.3. Immunogenicity (Anti-Drug Antibodies, ADA)

Blood samples for ADA analyses will be collected at the time points specified in Table 6.1 and Table 6.2. A blood sample will be drawn at each time point. Serum concentrations of DS-8201a and/or total anti-HER2 antibody may be measured using the same ADA samples for purpose of ADA assessment.

Instructions for the handling and shipping of ADA serum samples are included in a separate document (ie, Laboratory Manual). The ADA samples will be shipped to a central laboratory for forwarding to a Sponsor designated bioanalytical laboratory.

The immunogenicity testing will be performed using validated ADA assay following tiered assay steps including screening, confirmatory as well as titer determination. Samples confirmed positive will be banked until availability of the neutralizing anti-drug antibody (NAB) assay.

8.4. Pharmacogenomic Analysis

8.4.1. Tumor Sampling

In addition to the tumor sample required for confirmation of HER2 status, additional slides (up to 5) for exploratory biomarker analysis are requested (if the subject signs the additional optional informed consent form for Pharmacogenomics analysis). The detailed instructions for the handling of tumor samples and shipping of tumor samples are included in the Laboratory Manual.

8.4.2. Genomic or Genetic Banking and Analysis

A single blood sample for pharmacogenomics analysis will be collected from each subject, who consented to this test, before drug administration on Day 1 of Cycle 1. Participation in this part of the study is optional for all subjects.

The following procedures will be used for the long-term preservation (banking) of DNA specimens extracted from subjects' blood samples. Pharmacogenomic samples may be analyzed for genes involved in absorption, distribution, metabolism, elimination, safety, and efficacy of DS-8201a. Additionally, samples may be analyzed for genes involved in DS-8201a related signaling pathways, or to examine diseases or physiologic processes related to DS-8201a DNA samples will not be immortalized or sold to anyone. This information may be useful in increasing the knowledge of differences among individuals in the way they respond to the study drug, as well as helping in the development of new drugs or improvement of existing drugs.

Specimen shipping and handling details will be included in the Laboratory Manual.

8.4.2.1. Disclosure of the Results of Genomic or Genetic Analysis

Because the nature and value of future pharmacogenomic research cannot be known at this time, any results obtained from research involving pharmacogenomic samples will not be disclosed to the subject or investigators now or in the future.

8.4.2.2. Storage and Disposal of Specimens for Genomic or Genetic Banking and Analysis

Samples will be retained until exhausted or until the Sponsor requests disposition.

If the subject withdraws consent, the banked blood samples will be promptly managed regarding proper disposition. However, the data will not be discarded if genetic analysis has been completed before the subject withdraws consent.

8.5. Biomarker and Exploratory Variables

Exploratory biomarkers such as HER2EDC in serum may be measured by a central laboratory. Other exploratory biomarkers in tumor tissue or blood such as cfDNA in plasma may be measured.

9. SAFETY EVALUATION AND REPORTING

9.1. Adverse Event Collection and Reporting

All clinical AEs (see Section 9.4.1 for definitions) occurring after the subject signs the ICF and up to 40 (+ 7) days after last treatment (ie, the follow-up period), whether observed by the investigator or reported by the subject, will be recorded on the Adverse Event CRF page. All SAEs occurring after subject signs the ICF and up to 40 (+ 7) days after last treatment will be recorded on CRF. Medical conditions (including laboratory values/vital signs that are out of range) that were diagnosed or known to exist prior to Informed Consent will be recorded as part of medical history.

All AEs, SAEs, and events of special interest are to be reported according to the procedures in Section 9.5.

All laboratory results, vital signs, and ECG results or findings should be appraised by the investigator to determine their clinical significance. Isolated abnormal laboratory results, vital sign findings, or ECG findings (ie, not part of a reported diagnosis) should be reported as AEs if they are symptomatic, lead to study drug discontinuation, dose reduction, require corrective treatment, or constitute an AE in the investigator's clinical judgment.

At each visit, the investigator will determine whether any AEs have occurred by evaluating the subject. Adverse events may be directly observed, reported spontaneously by the subject or by questioning the subject at each study visit. Subjects should be questioned in a general way, without asking about the occurrence of any specific symptoms. The investigator must assess all AEs to determine seriousness, severity, and causality, in accordance with the definitions in Section 9.4. The investigator's assessment must be clearly documented in the site's source documentation with the investigator's signature.

Always report the diagnosis as the AE or SAE term. When a diagnosis is unavailable, report the primary sign or symptom as the AE or SAE term with additional details included in the narrative until the diagnosis becomes available. If the signs and symptoms are distinct and do not suggest a common diagnosis, report them as individual entries of AE or SAE.

For events that are serious due to hospitalization, the reason for hospitalization must be reported as the SAE (diagnosis or symptom requiring hospitalization). A procedure is not an AE or SAE, but the reason for the procedure may be an AE or SAE. Pre-planned (prior to signing the ICF) procedures or treatments requiring hospitalization for pre-existing conditions that do not worsen in severity should not be reported as SAEs (see Section 9.4.2 for Definitions).

For deaths, the underlying or immediate cause of death should always be reported as an SAE. Disease progression is a study endpoint and consequently, should not be reported as an AE/SAE. However, when a subject dies from PD with no other immediate causes, "disease progression" should be reported as an SAE.

Any serious, untoward event that may occur subsequent to the reporting period that the investigator assesses as related to study drug should also be reported and managed as an SAE.

